4.0 Treatment Plan

4.1 General

All patients will be registered through CORE. The objective will be to administer azacitidine and sorafenib at full dose.

4.2 Schedule

PROTOCOL SUMMARY/SCHEMA

SCHEDULE OF EVALUATIONS / STUDY CALENDAR

Parameter	Pre-study	Weekly *****	Before Each Cycle	Before Every 2 - 4 Cycles	Study Termination	Follow - Up
History	X				X	X
Physical examination	X		X	X	X	X
BP**	X	X	X	X	X	X
Weight	X		X	X	X	X
Measurement of extramedullary tumor*****	X		X	X	X	X
Performance status	X		X	X	X	X
CBC, differential, platelet count	X	X	X	X	X	X
Serum Chemistries (must include, Bilirubin, Alk Phos, ALT orAST)	X	X	X	X	X	X
Glucose and Electrolytes (Na, K, Cl, CO ₂)	X	X	X	X	X	X
PT/PTT/INR***	X		X	X	X	X
Bone marrow exam with cytogenetics and molecular studies for FLT3 and NPM1****	X			X	X	
Beta HCG	X					
Chest x-ray	X					
Brain CT or MRI scan *	X					

As appropriate

*Brain imaging (CT/MRI) should be performed only in patients with neurological signs and symptoms concerning for intracranial metastatic masses.

**Blood pressure should be monitored weekly during the first 4 weeks of sorafenib therapy and thereafter monitored and treated, if required, in accordance with standard medical practice. In cases of severe or persistent hypertension, despite institution of antihypertensive therapy, temporary or permanent discontinuation of sorafenib should be considered.

***Infrequent bleeding events or elevations in the International Normalized Ratio (INR) have been reported in some patients taking warfarin while on sorafenib therapy. Patients taking concomitant warfarin should be monitored weekly for changes in prothrombin time, INR or clinical bleeding episodes.

****Bone marrow exam should be performed at Screening the end of Cycle 1, every 2-3 cycles for the first year, then at the discretion of the treating physician. Any change to this schedule that the treating physician feels is in the best interest of the patient must be approved by the PI.

Molecular studies (FLT3 and NPM1) performed at baseline only and on patients with unknown status.

***** Labs will be collected once weekly for the first 2 cycles, then monthly thereafter (differential can be omitted if WBC is $\leq 0.5 \times 10^9/L$)

*****Any tumor masses will be measured before and after the treatment to assess their response to treatment.

4.2.1 Patients will be treated according to the following schedule:

- Azacitidine 75 mg/m^2 will be administered subcutaneously (SQ) or intravenously (IV) daily for 7 days per cycle. Cycles should be repeated every 4-8 weeks at the discretion of the treating physician. The next azacitidine course may be started before 4 weeks or after 8 weeks if felt to be in the best interest of the patient and only after discussion with the PI.
- Sorafenib will be administered orally at a dose of 400 mg twice daily every day continuously. Sorafenib will only be held for sorafenib-related toxicity.

Both agents will start on the same day of the first cycle. Sorafenib will be given continuously thereafter unless there is a Sorafenib-related toxicity. It will be re-started as soon as that toxicity has resolved to a Grade 1 or baseline status. The first dose of each course of Azacitidine will constitute the beginning of the next cycle of treatment.

Dose reductions for both agents are allowed but should be discussed with the PI and documentation of the justification recorded in the chart.

One cycle of therapy is defined 7 days of azacitidine and continuous dosing of sorafenib. Patients will receive one cycle of therapy every 4 weeks (with a desired dose schedule of 4 week cycles) and can be delayed up to 56 days. If the treating physician feels that one or both of the drugs must be held for a longer period of time, then it must have PI approval.

Subsequent courses of azacitidine will be given if the ANC is equal or greater than $1.0 \times 10^9/L$ (or lower if the treating physician feels in the best interest of the patient and after discussion with PI) and the platelets are equal to or greater than $30 \times 10^9/L$ (unless transfusion dependent), in the absence of residual leukemia in the bone marrow (for the first 3 cycles of therapy, it is intended that the azacitidine cycles are administered every 4 weeks despite cytopenias and even if full recovery to the above levels has not occurred). If prolonged myelosuppression (more than 60 days) with evidence of a hypocellular marrow (marrow cellularity less than 5% without evidence of leukemia) is observed subsequent courses of azacitidine may be given at a lower dose after discussion with the PI. If the peripheral counts do not recover (ANC $< 1 \times 10^9/L$ (or to baseline value) and/or platelets $< 30 \times 10^9/L$ (unless transfusion dependent) but there is evidence of residual leukemia in the bone marrow, subsequent cycles can be administered earlier than 4 weeks at the

discretion of the treating physician, but not earlier than 3 weeks after the previous cycle.

Sorafenib is supplied as an immediate-release film-coated, round, and salmon color tablet containing 200 mg of the free base, Sorafenib, and the excipient croscarmellose sodium, microcrystalline cellulose, hydroxypropyl methylcellulose, sodium lauryl sulfate, and magnesium stearate. The film-coat consists of hydroxypropyl methylcellulose, polyethylene glycol, titanium dioxide and red iron oxide. The film coating has no effect on the rate of release of the active sorafenib.

Sorafenib will be administered 400 mg twice daily for 28 days/or until next cycle of Azacitidine is administered in each cycle. Drug doses must be separated by intervals of approximately 12 hours (+/-3 hours).

If a dose is missed, the next dose should not be increased to account for missing a dose. The subject should take the next regular dose at the regularly scheduled time. If a dose is vomited, do not take another dose of medication. Wait until the next dose is due. Take the next regular dose and do not increase it to account for missing a dose.

Modifications to the schedule and/or dose of both/either drugs that are thought to be in the best interest of the patient are allowed after discussion with and approval by the PI.

It is recommended that patients receive at least 3 cycles of therapy (as long as they are not clearly progressing and are tolerating it without significant toxicity) before deciding on termination of treatment. Patients will be eligible for efficacy assessment if they have received at least one full cycle of therapy (7 days of azacitidine and 28 days of sorafenib).

4.3 Duration of Therapy:

In the absence of treatment delays due to adverse events, treatment may continue until one of the following criteria applies:

1. Progressive disease
2. Intercurrent illness that prevents further administration of treatment,
3. Patient request or
4. General or specific changes in the patient's condition render the patient unacceptable for further treatment in the judgment of the investigator.

It is planned that up to a total of 24 cycles of therapy will be administered for patients deriving benefit from this regimen. Continuation of therapy for patients completing 24 cycles of therapy may be considered on a case by case basis after discussion with the PI.

A minimum of 1 full course (defined as the administration of azacitidine for 7 days and sorafenib for up to 28 days) will be required for a patient to be considered as having received an adequate trial to evaluate efficacy. All patients receiving at least one dose of any of the two drugs will be considered evaluable for toxicity.

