13.0 Statistical Considerations

This is a single arm study using the dosage level recommended from a previously conducted and published phase I/II study in patients with relapsed AML. The sample size is 52. The trial will be continuously monitored for efficacy and toxicity (non-hematological \geq grade 3). The method of Thall, Simon, and Estey will be used to perform interim efficacy and safety monitoring.¹⁴

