13.1 Efficacy

The primary endpoint is the overall response (CR+CRi) after three cycles of treatment. The historical data suggested the overall response rate is 45%. With the assumption that the improved overall response rate to be 65%, it is estimated that a total of 52 evaluable patients will yield 83% power at a significance level of 5% based on chi-square test. The trial will be continuously monitored. The study will be stopped early if the data suggest that:

$$\Pr(\pi > 0.45 | \text{data}) < 0.05$$

Here π is the overall response (OR) rate. That is, if at any time during the study we determine that there is a less than 5% chance that the average OR rate is greater than 45%, we will terminate the study. The OR rate is assumed to follow a non-informative prior of Beta (0.9, 1.1).

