13.3 Analysis method

Data analysis will be performed using SAS or S-plus, as appropriate. All patients who received at least 1 dose of the combined agents will be included in the intent-to-treat analysis for efficacy. Demographic and disease characteristics of the patients at registration will be summarized using descriptive statistics such as mean, standard deviation (SD), median and range. Overall response rates will be presented with 95% confidence intervals. The association between response and patient and disease characteristics will be examined by two-sample t-test or Chi-square test.

The data from all patients who received the combined therapy during the study will be included for safety analysis. Subjects who entered the study and did not take any of the study drugs and had this confirmed will not be evaluated for safety. The severity of the toxicities will be graded according to the NCI CTCAE v4.0 whenever possible. We will follow standard reporting guidelines for adverse events. Safety data will be summarized by category, severity and frequency. The proportion of patients with AEs will be estimated, along with the Bayesian 95% credible interval. These descriptive summaries will be provided for all patients for each safety parameter by cycle, grade, and relationship to treatment.

This study will be conducted as described in this protocol, except for an emergency situation in which the protection, safety, and wellbeing of the patient requires immediate intervention, based on the judgment of the investigator or his/her designee. In the event of a significant deviation from the protocol, the investigator will notify the MDACC surveillance committee following the institutional guidelines.

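### Two rules on who counts for efficacy (at least one full cycle in 4.2.1 and 4.3, at least one dose in 13.3) are not reconciled, and neither the 52 evaluable patients in 13.1 nor the patient count in Table 13.1 is tied to either

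*Combined protocol and SAP*

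**What the plan says.** Three places say who counts for efficacy.

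- **Section 4.2.1:** patients are "eligible for efficacy assessment if they have received at least one full cycle of therapy (7 days of azacitidine and 28 days of sorafenib".
- **Section 4.3:** one full course "will be required for a patient to be considered as having received an adequate trial to evaluate efficacy". The course is "defined as the administration of azacitidine for 7 days and sorafenib for up to 28 days", so the sorafenib part is a ceiling here and a fixed duration in 4.2.1.
- **Section 13.3:** "All patients who received at least 1 dose of the combined agents will be included in the intent-to-treat analysis for efficacy". It adds: "Overall response rates will be presented with 95% confidence intervals".

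For toxicity, 4.3 says: "All patients receiving at least one dose of any of the two drugs will be considered evaluable for toxicity". Section 13.3 agrees in substance: it leaves out of the safety evaluation only patients confirmed to have taken no study drug.

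On size, 13.0 says "The sample size is 52" without qualification, while 13.1 says that "a total of 52 evaluable patients will yield 83% power". Table 13.1 has a single patient-count column that serves both the response limits and the toxicity limits. Being evaluable is defined for toxicity, and 4.2.1 and 4.3 set the efficacy condition. Nothing links the 52 in 13.1 or the rows of Table 13.1 to the full-cycle set or to the at-least-one-dose set.

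**The concern.** The primary result is a single-arm CR+CRi rate compared with a fixed 45%, so the denominator matters directly. A patient who dies or withdraws before completing any full cycle stays in the 13.3 set as a non-responder but drops out under 4.2.1 and 4.3. Dropping such patients raises the rate unless they would have responded as often as the others. A literal 28 days of sorafenib could also remove a responder whose sorafenib was held, so the direction is likely but not guaranteed.

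The same ambiguity reaches the interim rules. If response is counted in full-cycle patients and toxicity in all dosed patients, the two limits in one row of Table 13.1 apply to different numbers of patients. Because the text supports two denominators, the choice could be made after the data are seen.

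**Working it through.** **1. The plan's own figures.** Inputs from 13.1: null 45%, alternative 65%, n = 52, 5% level, chi-square test, sidedness not stated. Two-sided, one-sample normal power is

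Φ[(0.20 − 1.96·√(0.45·0.55/52)) / √(0.65·0.35/52)] = Φ[(0.20 − 1.96·0.0690)/0.0661] = 83.6%.

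The exact version of that rule passes at 31 or more of 52: P(X ≥ 31) is 83.2% at 65% and 2.4% at 45%. One-sided, the rule would be 30 or more, with 89.3% power, so the two-sided reading matches the stated 83%. All Table 13.1 limits reproduce from the Beta(0.9, 1.1) and Beta(0.6, 1.4) priors. The arithmetic is sound for any 52 patients; the open question is which 52.

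**2. Effect on a final result.** Take 29 responses among 52 treated, 5 of the non-responders having no full cycle (exact 95% intervals).

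- All treated: 29/52 = 55.8%, CI 41.3–69.5%, which includes 45%; below the 31 needed.
- Full-cycle only: 29/47 = 61.7%, CI 46.4–75.5%, which excludes 45%; above the 28 needed at n = 47.

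**3. Chance of passing at a true all-treated rate of 45%.** Let d be the share excluded and q the response rate among them. The rate among those kept is (0.45 − d·q)/(1 − d). For d = 0.10 and q = 0.20 it is (0.45 − 0.02)/0.90 = 47.8%. With 52 evaluable patients accrued, P(X ≥ 31) is as follows. The documents give neither d nor q; both are assumptions.

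| Excluded (d) | q = 30% | q = 20% | q = 0 (upper bound) |
|---|---|---|---|
| 5% | 3.1% | 3.7% | 5.2% |
| 10% | 4.2% | 5.8% | 10.6% |
| 15% | 5.6% | 9.1% | 20.5% |
| 20% | 7.6% | 14.3% | 36.6% |

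With nobody excluded the figure is 2.4%. Futility stops are ignored here; including them changes little (35.9% instead of 36.6% in the last cell).

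**4. Futility at a true all-treated rate of 35%.** Exact recursion over the response limits alone, in cohorts of 4, gives a 58% chance of stopping if all treated are counted. At 10% and 20% excluded it falls to 56% and 52% (q = 30%), 50% and 41% (q = 20%), or 41% and 23% (q = 0).

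**5. One interim look for response.** The posterior after x responses in n is Beta(0.9 + x, 1.1 + n − x).

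- 5/20: Pr(π > 0.45) = 0.035, below 0.05, so the trial stops.
- If two of those 20 are non-responders without a full cycle, the count is 5/18 with posterior 0.071. Table 13.1 has no row for 18, so the decision waits for 20 full-cycle patients. It is then a stop only if neither of the next two responds, since 6/20 is above the limit of 5.

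**6. The toxicity column.** The posterior is Beta(0.6 + x, 1.4 + n − x). The row for 20 stops at 10 toxicities, where Pr(P_E > 0.3) = 0.961. If that row is reached with 20 full-cycle patients but toxicity is counted in 22 dosed patients, 10/22 gives 0.924. The table would then stop the trial short of its own 0.95 criterion.

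**7. Power if 65% describes full-cycle patients only.** With 52 treated and all counted, the rate is 0.65(1 − d) + d·q. At d = 0.10 and q = 0 it is 58.5%, and P(X ≥ 31) = 49%. At d = 0.10 and q = 20% it is 60.5%, and power is 61%.

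**The case against.** The strongest reply is that 13.3 settles the matter. It is the only analysis-method text, it names one efficacy set, and it calls the analysis intent-to-treat; the full-cycle rule can stand beside it as a secondary evaluable set. For the final rate this largely holds, so steps 2 and 3 describe the less natural reading. A reader might infer that the final analysis will exclude early failures, and the documents do not support that. What survives is that 13.3 neither calls its analysis primary nor says that it overrides 4.2.1 and 4.3, and that it is silent on the interim count. The power statement speaks of evaluable patients, which sits closer to 4.2.1 and 4.3.

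A second reply is that missing assessments are already handled: CR and CRi in Section 9 require marrow and blood-count criteria, so an unassessed patient cannot be a responder. That is right only for patients kept in the denominator.

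Three further inferences go too far.

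- **Any incomplete first cycle excludes a patient.** The rule is at least one full cycle, so a later one qualifies. Under the 4.3 wording, stopping sorafenib early may not exclude anyone who completed azacitidine.
- **Early toxicities would be dropped.** Sections 4.3 and 13.3 keep every dosed patient in the toxicity count. The mismatch in step 6 leads to earlier stopping and hides no harm. The written rule can also be computed directly at 22 patients.
- **The futility decision is reversed.** Step 5 shows a stop that is delayed and may not occur.

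The pass rule is also reconstructed: 13.1 mentions the chi-square test only for power, and 13.3 promises a rate with an interval. The 29/47 example is deliberately close to the threshold.

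**Conclusion.** The point holds as an unreconciled definition that should be fixed. The full-cycle rule and the at-least-one-dose rule both stand in the current text, and the sample size and monitoring table are tied to neither. A reader might conclude that the 83% power or the stopping limits are wrong; they reproduce, and no arithmetic error is alleged.

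If the full-cycle rule were applied with 52 evaluable patients, the chance of passing at a true all-treated 45% would rise from 2.4% to 3.1–7.6%, 3.7–14.3% or 5.2–36.6% over 5–20% excluded, as 30%, 20% or none of the excluded respond. Futility stopping at a true 35% would weaken correspondingly. These figures rest on assumed exclusion and response rates and on a two-sided 5% score rule inferred from the stated power; the none-responding figures are upper bounds. If exclusions are few, or the excluded respond nearly as often as the rest, the effect is small.

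**What to change.** Reconcile 4.2.1, 4.3, 13.1, 13.3 and the header of Table 13.1:

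- Make the treated set of 13.3 the single primary efficacy set for the estimate, the test and the response column of Table 13.1. State that it takes precedence over 4.2.1 and 4.3.
- Say whether one dose of the combined agents means either drug or both. Adopting the either-drug wording that 4.3 uses for toxicity gives both columns of Table 13.1 one count.
- Count patients with early death, withdrawal or no response assessment as non-responders. Classify patients with a sorafenib interruption by their actual response.
- Keep one full-cycle definition, worded once, as a labelled sensitivity analysis.
- In 13.1, replace evaluable with treated, and state which population the 45% and the 65% refer to.

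The cost is wording, with no new data. The reported rate may be less favourable (55.8% instead of 61.7% in the example). N = 52, the boundaries and the 83% power stand if 45% and 65% apply to all treated patients. If 65% was meant for full-cycle patients only, the target or the sample size must be restated, because power with 52 treated would be about 49% at 10% excluded with none of them responding.

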4.4 Concomitant medications

In general, the use of any concomitant medication/therapies deemed necessary for patient supportive care and safety are permitted. Other anticancer agents including systemic chemotherapy, radiation therapy, or biologic response modifiers are not permitted during the study. No other investigational drug is allowed during the study. Patients must be off growth factors for five days in order to declare a neutrophil response. Prophylaxis may be used for the prevention of nausea and vomiting. Patients may be given ondansetron up to 3 times a day or granisetron up to 2 times a day. Ondansetron and granisetron are federally approved drugs and will not be supplied by Bayer/Onyx or Celgene. Patients who suffer from Grade 3 or 4 nausea and/or vomiting, should be withheld from treatment and only restart if recovery occurs when symptoms are controlled to a Grade 1 status. Other antibiotics may be used at the discretion of the investigator include, but are not limited to, metoclopramide, promethazine, cyclizine, and prochlorperazine.

In the event of severe anemia, thrombocytopenia or neutropenia, patients may receive appropriate supportive care (e.g., transfusions, prophylactic antibiotics, antifungals and/or antivirals, hematopoietic growth factors). In the event of high white blood cell (WBC) counts, patients may receive hydroxyurea or up to 2 doses of ara-C prior to start of study medication in order to keep their WBC at an acceptable level. During the trial they may undergo Leukapheresis or receive further doses of hydroxyurea for the same purpose (if necessary).

Concomitant administration of any other therapy specific for MDS, CMML or AML, including any use of systemic retinoids, is prohibited. Concomitant administration of any other anticancer therapy is prohibited. Intrathecal chemotherapy is allowed, when indicated.

Subjects may receive anti-infective prophylaxis including azoles according to institutional practices. Use of recombinant myeloid colony stimulating factors (CSF) is allowed, if patients have febrile neutropenia or documented infections. The use of strong CYP3A4 inducers are not allow.

5.0 Dosing Delays/Dose Modifications

Patients experiencing unacceptable toxicity directly attributable to the study drugs should temporarily stop treatment according to the guidelines in the dose adjustment schema.

Toxicity grading will be according to the NCI CTCAE, v4. To prevent unnecessary morbidity, the following guidelines for dose adjustment for drug-related toxicities are recommended.

Dose Reductions for non-hematologic toxicity possibly related to study drugs should be performed according to the following table:

Toxicity	Grade	Actions
Non-hematological (excludes myalgia/arthralgia responding to treatment, inadequately treated vomiting and diarrhea, or electrolyte abnormalities unless not responding to optimal supplementation)	3 or 4	Hold therapy until recovery to Grade ≤ 1 , then re-start and reduce one dose level unless approved by PI on case to case basis. If toxicity recurs again, hold therapy until recovery to grade ≤ 1 , then re-start and reduce one dose level. Dose reductions below dose level -2 will be considered on an individual basis after discussion with the PI. For grade 4, the recommendation is to discontinue Sorafenib
Non-hematological (excludes myalgia/arthralgia responding to treatment, inadequately treated vomiting and diarrhea, or electrolyte abnormalities unless not responding to optimal supplementation)	Persistent 2-considered clinically significant or upon patient's request	Hold therapy until recovery to Grade ≤ 1 , then re-start and reduce one dose level unless approved by PI on case to case basis. If toxicity recurs again, hold therapy until recovery to grade ≤ 1 , then re-start and reduce one dose level. Dose reductions below dose level -2 will be considered on an individual basis after discussion with the PI.

Patients in whom the toxicity occurs or persists beyond the planned completion of drug administration for the cycle will have the dose reductions implemented in subsequent cycles provided the toxicity has resolved as specified in the table above.

5.1 Myelosuppression:

Patients with leukemias and MDS usually present with abnormal peripheral blood counts at the time therapy is started and myelosuppression is an expected event during the course of therapy for acute leukemias and myelodysplastic syndromes. Thus, no dose adjustments or treatment interruptions for myelosuppression will be planned for the first 4 weeks of therapy. After this time, treatment interruptions and dose adjustments may be considered according to the following guidelines:

Patients with neutropenia or thrombocytopenia as a consequence of the disease, do not require treatment interruptions for myelosuppression. Dose-reductions in these patients should be considered in an individual case after discussion with the PI. The following guidelines can be used for these patients:

Patients with a response and pre-cycle counts of neutrophils $> 1 \times 10^9/L$ and platelets $>30 \times 10^9/L$ who have sustained low counts of neutrophils $<0.5 \times 10^9/L$ or a platelet count $<20 \times 10^9/L$ for more than 2 consecutive weeks in the current cycle, may receive a subsequent course. A reduction of up to 2 dose levels may be considered if the myelosuppression was deemed severe and life threatening by the treating physician, and if it is in the patient's best interest after discussion with the PI.

If there are persistent peripheral blood blasts, or the bone marrow shows $>5\%$ blasts, continue treatment regardless of neutrophil and platelet count and give supportive care as needed. After 3 cycles, there should be clear evidence of benefit (reduction in bone marrow blasts, improving counts with reduction in transfusion requirement or other clinical improvement in the opinion of the treating physician) in order to continue treatment regardless of the counts.

If no marrow evidence of leukemia, may hold therapy with azacytidine until recovery of granulocytes to $\geq 1 \times 10^9/L$ and platelets $\geq 30 \times 10^9/L$, then resume at same or 1 lower dose level according to guidelines mentioned above. In general, in the absence of other toxicity, it is recommended that therapy with sorafenib is not interrupted in a responding patient even in the presence of cytopenias (unless discussed with PI).

5.2 Dose escalation:

Dose escalation of sorafenib to 600 mg twice daily will be permitted provided:

- Patient has not experienced any grade 3 or higher non-hematologic toxicity, and
- Patient has not experienced hematologic grade 4 toxicity believed to be treatment related, and
- This has been discussed and approved by the PI and recorded in the patient's clinical records

Dose reductions/modifications/delays:

Dose reductions for sorafenib-specific non hematologic toxicity during subsequent cycles should be performed according to the table in section 5.3 above. Dose modification suggestions for specific toxicities can be found below.

Dose reduction to 200 mg twice daily, 200 mg once daily, and then 200 mg every other day will be allowed depending on the type and severity of toxicity encountered, provided that criteria for patient withdrawal from study treatment have not been met. The following tables describe the recommended dose modifications for sorafenib-associated toxicities:

Variation in the dosing schedules discussed may be allowed if thought to be in the best interest of the patient and after discussing with the study PI.

Suggested dose levels for each drug (adjustments to the dose of each drug can be done independently of the other):

Dose level	Sorafenib	Dose level	Azacytidine
-2	200 mg po daily	-2	50 mg/m ² SC/IV daily x 3
-1	200 mg po bid	-1	50 mg/m ² SC/IV daily x 5
0	400 mg po bid	0	75 mg/m ² SC/IV daily x 7
+1	600 mg po bid	+1	None

Proposed Dose modification for Sorafenib Associated toxicity

Table 1: Suggested Dose Modifications for Sorafenib for Hand-Foot Skin Reaction

Skin Toxicity Grade	Occurrence	Suggested Dose Modification
Grade 1 Numbness, dysesthesia, paresthesia, tingling, painless swelling, erythema or discomfort of the hands or feet which does not disrupt the patient's normal activities	Any Occurrence	Continue treatment with Sorafenib and consider topical treatment for symptomatic relief.
Grade 2 Painful erythema and swelling of the hands or feet and/or discomfort affecting the patient's normal activities	1 st Occurrence	Continue treatment with Sorafenib and consider topical treatment for symptomatic relief. If no improvement within 7 days see below
	No improvement within 7 days or 2 nd or 3 rd occurrence	Interrupt Sorafenib until toxicity resolves to Grade 0-1. When resuming treatment, decrease by 1 dose level
	4 th occurrence	Discontinue Sorafenib treatment
Grade 3 Moist desquamation, ulceration, blistering or severe pain of the hands or feet, or severe discomfort that causes the patient to be unable to work or perform activities of daily living	1 st or 2 nd occurrence	Interrupt Sorafenib treatment until toxicity resolves to Grade 0-1. When resuming treatment decrease Sorafenib by 1 dose level
	3 rd Occurrence	Discontinue Sorafenib treatment

At first occurrence of HFSR, independent of grade, prompt institution of supportive measures such as topical emollients, low potency steroids, or urea-containing creams should be administered.

Table 2: Dose Modifications for Sorafenib-Associated Toxicity¹

Toxicity	Grade 1	Grade 2	Grade 3*	Grade 4*
Non-hematologic	Continue at the same dose level.	Reduce and Continue at the same dose level.	Withhold ^b dose until toxicity is grade ≤ 1 , then resume treatment decreasing by 1 dose level. If patient experiences a second grade 3 toxicity, withhold ^b dose until toxicity is grade ≤ 1 , then reduce dose by an additional dose level	Discontinue protocol therapy
a. Also excludes nausea/vomiting that has not been pre-medicated, and diarrhea b: If no recovery after 60 day interruption, treatment should be discontinued unless subject is deriving clinical benefit c: If more than 2 dose reductions are required, treatment should be discontinued.				
Toxicity	Grade 1	Grade 2	Grade 3*	Grade 4*
Hematologic	Continue at the same dose level.	Continue at the same dose level.	Withhold dose until toxicity is grade ≤ 2 , then resume treatment decreasing by 1 dose level ^b . If patient experiences a second grade 3 toxicity, withhold dose until toxicity is grade ≤ 2 , then reduce dose by an additional dose level	Withhold ^a dose until toxicity is grade ≤ 2 , then reduce dose by 2 dose levels ^b and resume treatment, or discontinue at the discretion of the principal investigator after discussion with study supporter.

a. If no recovery after 28 day delay, treatment should be discontinued

b. If more than 2 dose reductions are required, treatment should be discontinued.

Hypertension:

Hypertension is a known and potentially serious adverse event associated with Sorafenib treatment. Patients will have their blood pressure monitored and recorded weekly during the first cycle of therapy, either at the doctor's office or by using any calibrated electronic device (such as those found at a local drug store or pharmacy). Patients will have a Blood Pressure Diary on which to record the measurements, which will be kept with research chart. If the patient's blood

pressure is sustained at an elevated level at any time (>150/100), they should contact their treating physician.

Blood pressure measurements considered out of the normal range are diastolic pressure > 90 mm Hg and/or systolic pressure > 150 mm Hg, or a 20 mm Hg increase in diastolic pressure if the previous measurement was within normal limits.

The dose-modification schedule to be followed in the event of treatment-induced hypertension is outlined in Table 3. **The choice of anti-hypertensive medication to be used in cases of treatment-induced hypertension will be at the investigator's discretion and based on site-specific treatment guidelines as applicable.** All anti-hypertensive medications used for the management of treatment-emergent hypertension should be recorded in the subject's eCRF.

Table 3 Dose Modifications of Sorafenib for Hypertension

Grade (CTCAE v4.0)	Antihypertensive Therapy	Blood Pressure Monitoring	Sorafenib Dose
Grade 1 Pre-hypertension (systolic BP 120-139 mm Hg or diastolic BP 80-89 mm Hg)	None	Consider increased BP monitoring	No change
Grade 2 (asymptomatic) systolic BP 140-159 mm Hg or diastolic BP 90-99 mm Hg	Begin anti-hypertensive therapy as prescribed by the investigator based on site-specific treatment guidelines as applicable.	Increase frequency and monitor (by health professional) every 2 days until stabilized	No change
Grade 2 recurrent or persistent (> 24 hrs); symptomatic increase by 20 mm Hg(diastolic)/ OR Diastolic BP > 90 mm Hg and systolic > 140 mm Hg if previously WNL OR Grade 3	Add agent(s): as prescribed by the investigator based on site-specific treatment guidelines as applicable	Increase frequency and monitor (by health professional) every 2 days until stabilized; continue qod monitoring to stabilization after dosing restarted.	Hold ^a Sorafenib until symptoms resolve and diastolic BP < 90 mm/Hg. Resume treatment at 1 dose level lower ^b . If diastolic not controlled (< 90) on therapy, reduce another dose level ^c
Grade 4 Life Threatening			Off protocol therapy

- ^a Subjects requiring a delay of > 28 days should go off protocol therapy.
^b May be able to resume full dose later once blood pressure is adequately controlled.
^c Subjects requiring > 2 dose reductions should go off protocol therapy.

CTCAE v4.0 definitions

Grade 1: Prehypertension (systolic BP 120-139 mm Hg or diastolic BP 80-89 mm Hg)
Grade 2: Stage 1 HTN (systolic 140-159 mm Hg or diastolic BP 90-99Hg, medical intervention indicated; recurrent or persistent (>24 hrs) or symptomatic increase by >20 mmHg (diastolic) or to > 140/90if previously WNL; monotherapy indicated.
Grade 3: Stage 2 HTN (systolic BP > = 160 mm Hg or diastolic BP > = 100 mm Hg): medical intervention indicated; requiring more than one drug or more intensive therapy than previously
Grade 4: life threatening (e.g., malignant hypertension, transient or permanent neurologic deficit, hypertensive crisis)

Patients who develop GI perforation should discontinue therapy and be taken off study.

